7.3.1 Adverse Event Severity Rating

The following categories of adverse event severity are to be used:

Mild	Awareness of sign or symptom that does not interfere with the subject's usual activity or is transient, resolved without treatment and with no sequelae.
Moderate	Interferes, but does not hinder, the subject's usual activity and/or may require treatment.
Severe	Symptom(s) causing severe discomfort and significant impact on the subject's usual activity and requires treatment or intervention.

7.3.2 Causality Rating

The causal relationship to study device will be evaluated as follows:

Definitely Related	The adverse event is clearly related to the test product.
Probably Related	The adverse event is temporally associated and plausibly related to the product/procedure but there are also potential alternative explanations, though the alternatives are not likely.
Possibly Related	The adverse event may be related, scientifically plausible, but there are also alternative explanations.

8 REPORTING OF DEVICE DEFICIENCIES / TECHNICAL OBSERVATIONS

In case device malfunctions occur, they will be reported to NovaSignal within 10 business days. The report should include at a minimum, a description of event, date of occurrence, lot or serial number of the device.

A study device has malfunctioned if it meets the following definition: The failure of a device to meet its performance specifications or otherwise perform as intended. Performance specifications include all claims made on the labelling for the device. The intended performance of a device refers to the intended use for which the device is labelled.

Classification	Reporting time	Type of report
Unanticipated Adverse Device Effects (UADE)	Notify NovaSignal within 1 business day of learning of event. Notify IRB as required.	Device Related Serious Adverse Event Report Form
Serious Device Related Adverse Events (related to the performance of the study device)	Notify NovaSignal within 1 business day of learning of event. Notify IRB as required.	Device Related Serious Adverse Event Report Form
Study Device Deficiency/Malfunction – NOVAGUIDE with or without Adverse Event	Notify NovaSignal within 10 business days of learning of event. Notify IRB as required.	Device Deficiency/Malfunction Form

9 PROTOCOL DEVIATIONS

A protocol deviation is defined as a study related activity that is not in compliance with the protocol. Examples of deviations include but are not limited to a required test not being done or not being done within the specified timeframe, a subject enrolled who did not meet the inclusion/exclusion criteria, or enrolment of a subject without appropriate consent.

Deviations from the protocol must be reported to NovaSignal.

Protocol deviations can be classified into one of the three categories:

- Class I: Was intended to protect the life and physical well-being of the subject in an emergency.
- Class II: Was a non-emergency situation but the deviation was beyond the investigator's control.
- Class III: Was a non-emergency situation and was within the investigator's control. This deviation must be reported to NovaSignal in a timely manner.

10 QUALITY CONTROL AND QUALITY ASSURANCE

10.1 Organizational Preparations

A site evaluation via personnel and facility documentation will be performed by NovaSignal or their designee during the study to ensure the availability of appropriately trained personnel to conduct the study according to the FDA Code of Federal Regulations and ICH Guidelines on Good Clinical Practices (ICH-E6). This study will be conducted under the principles described in the Declaration of Helsinki.

10.2 Training

NovaSignal will provide training for the use of the NovaGuide System, in adherence to the Instructions for Use/ User Manual. Documentation of training should be maintained by the Principal Investigator throughout the study.

10.3 Data Quality Assurance

Training of appropriate site personnel will be the responsibility of NovaSignal or designee. To ensure uniform data collection and protocol compliance, site personnel will utilize source documentation worksheets to document protocol procedures.

10.4 Subject Privacy

All data will be maintained under highly secure and fully HIPAA-compliant dedicated servers under the direction supervision of the Principal Investigator. Primary data that is obtained will have identifying information and will be stored securely onsite. Access to identifiable subject data is limited to project staff who have direct data management and/or statistical responsibilities, under the direct supervision of the Principal Investigator.

The study participant's contact information will be securely stored at each clinical site for internal use during the study. At the end of the study, all records will continue to be kept in a secure location for as long a period as dictated by the reviewing IRB.

Data de-identification will be performed manually using the "safe-harbor" approach under the supervision of the Principal Investigator. At this point, a unique ID is generated for each subject, and each exam. These will populate two databases using the "safe-harbor" approach under the supervision of the Principal Investigator. The database that is devoid of all PHI will be used for data analysis in this research.

10.5 Case Report Forms

All required data for this study will be collected on standardized Case Report Forms (CRF). The forms may be paper based or electronic. The forms will only include the subject study number assigned once the subject is screened. The investigator is responsible for the accuracy, completeness and legibility of the data reported to NovaSignal in the CRFs and in all required reports. The CRFs are to be dated and signed by an investigator on appropriate pages to verify that he/she has reviewed the recorded data.

10.6 Investigational Device Accountability

The NovaGuide System specific serial numbers must be documented at a study site by a designated person, handled and stored properly in a secured location in which only the study staff have access. The Principal Investigator must maintain an accurate record of the status of the products throughout the study. Investigators are responsible for appropriate logging of the devices used, verification of packing slip information (i.e. lot numbers and quantity shipped), date and identity that each device was used in the study, disposition information regarding disposal or return to the Sponsor.

10.7 Selection of Investigators

The study will be conducted at multiple centers. Study staff for each center will meet the following criteria:

- A user trained by NovaSignal in the use of the Lucid M1 System and NovaGuide System.
- Commitment from the participating investigator to pursue details of any potentially device related adverse event outcomes
- Commitment from the participating investigator to enroll only subjects meeting the local approved protocol
- Dedicated staff members who can collect data and be willing to perform necessary documentation (e.g. CRF)

10.8 Close-out Document Review

The purpose of the final document review is to collect all outstanding study data documents, ensure that the principal investigator's files are accurate and complete, review record retention requirements with the principal investigator and ensure that all applicable requirements are met for the study.

The investigator agrees to allow the monitoring of study data, the completion of all data clarification or audits even after study close-out visit has been performed at NovaSignal' request.

11 STATISTICAL ANALYSIS

11.1 Phase 1 Statistical Analysis:

Primary Endpoint Analysis: Demonstration of VCI diagnostic performance at or exceeding 85% ROC-AUC (targeting SEN greater than 90%) to standard of care imaging.

Biomarker Validation and Analysis: VCI will be computed for each subject according to the procedure outlined in section 3.5, and group differences will be assessed using appropriate statistical methods. ROC-AUC will be computed detailing separability between groups for comparison to standard of care imaging (CTA) and prehospital/neurological clinical scales, along with SEN, SPE, and accuracy at various levels of diagnostic threshold, including that corresponding to Youden's maximal J-statistic.

Sample size calculation: From the results of our feasibility study, we estimate that expected effect size between VCI distributions for LVO (cohort A) and IHC groups (cohort B) will be large (Cohen's $D > 1.25$), such that only a small number of subjects in each group ($N = 11$) will be sufficient to detect significant differences (alpha of 0.05) with standard statistical power of 80%. However, in Phase 1 we seek to demonstrate the stronger aim of biomarker diagnostic performance in excess of 85% ROC-AUC. Assuming this target AUC is met, then sample size determines the confidence bounds on that estimate. In Phase 1 we require a sample of sufficient size to power confidence in the superiority of VCI diagnostic performance relative to current clinical prehospital stroke assessment scales. As existing preclinical scales top out at 78% AUC, this can be accomplished with a sample of roughly 50 subjects in each patient group, which gives a one-tailed 95% confidence bound on the target 85% AUC of less than 7%. The specification of 54 subjects per group is a target number intended to guarantee acquisition of a sufficient sample assuming at least 90% of target enrollment.

Initial safety endpoint analysis: Throughout the study we will collect adverse events, which will be used to determine the safety of the device within the acute stroke environment. In our EXPEDITE study which is also run in the ER for stroke assessment, the device has been designated minimal risk by the IRB and we have not had any serious adverse events in over 80 subjects. We will continue to closely monitor this metric.

In this work, we will also measure “Get with the Guidelines, Stroke” metrics from each site and compare them to literature, national and site metrics. This will enable us to demonstrate that the system does not adversely affect standard of care for subjects suspected of stroke. The reason we believe it will not affect standard of care is because the device will be used after initial CT and IV-tPA is administered, while the subject is waiting for CTA or intervention. The time window, although short, is available to allow us to measure both the TCD waveform and CTA to confirm VCI is an effective biomarker. Additionally, the times will be compared against the randomized groups (Cohort C and D).

Door to diagnostic imaging. (Statistical demonstration that show we will not delay anything when adding our NovaGuide workflow to), e.g. “Get with the Guidelines, Stroke”: We will calculate the following for subjects that have NovaGuide measurements:

- IV rt-PA arrive by 2 hour, treat by 3 hour: Percent of acute ischemic stroke patients who arrive at the hospital within 120 minutes (2 hours) of time last known well and for whom IV t-PA was initiated at this hospital within 180 minutes (3 hours) of time last known well.
- % Door to CT \leq 25 minutes: Percent of patients who receive brain imaging within 25 minutes of arrival.
- Door to Puncture (DTP) Time within 90 minutes: (Percentage of patients with acute ischemic stroke who receive mechanical endovascular reperfusion)

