2 BACKGROUND AND RATIONALE OF STUDY

The incidence of Large Vessel Acute Ischemic Stroke (AIS) has been estimated to be approximately 250,000 patients per year in the United States and is the leading cause of disability and fifth leading cause of death. Although endovascular interventions (stentriever) and pharmaceutical (tPA) treatments exist for large vessel occlusion (LVO), their use is limited due to the short time window from symptom onset during which these treatments are indicated to be administered. Moreover, recent estimates suggest only approximately 10% of eligible patients receive interventional treatment which has shown to lead to better outcomes in several world-wide RCTs. Currently, the gold standard for stroke diagnosis is CT angiogram (CTA) which is limited to in-hospital use or a low number of mobile stroke ambulances, all costing multi-millions of dollars, requiring expert operators and IV injection of iodine-rich contrast material. Additionally, the clinical stroke assessment scales (RACE, LAMS, CPSS) used in the field, although low cost and non-invasive, have proven unreliable due to training requirements and low inherent accuracies, with SEN and SPE ranging in a recent study from 0.50-0.64 and 0.83-0.92, respectively[13,14]. In order for intervention to be successful, a standardized, quantitative, field based (prehospital and pre-CTA) diagnostic tool is needed to improve LVO identification and ensure rapid transfer to a capable medical facility.

Goals. Establish clinical viability of a fully automated, non-invasive transcranial Doppler (TCD) derived biomarker based on cerebral hemodynamics for prehospital LVO assessment.

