4.2 Study Endpoints

4.2.1 Phase 1 Study Endpoints

Phase 1 Primary Endpoint:

- Area Under the Curve (AUC), Sensitivity, and Specificity of VCI when compared against standard of care CTA imaging for large vessel occlusion assessment.

Phase 1 Secondary Technical Efficacy Endpoint:

- Area Under the Curve (AUC), Sensitivity, and Specificity of a novel machine learning (ML) algorithm when compared against standard of care CTA imaging for large vessel occlusion assessment.
- VCI and experimental ML algorithm compared to prehospital/neurological clinical scales for alternative diagnostic criteria.

Phase 1 Primary Safety Endpoint:

- Incidence of device-related serious adverse events
- Last Known Normal (LKN) to First Hospital Arrival (Initial Door-In) time
- Door to Initial CT imaging (non-contrast) time
- Door to IV-tPA time
- Door to Initial CTA Acquisition time
- Door to Groin Puncture time
- CTA Acquisition to Groin Puncture time

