11.2 Phase 2 Statistical Analysis

Primary Endpoint Analysis: Demonstration of VCI biomarker performance at or exceeding 90% ROC-AUC (targeting SEN & SPE greater than 90%) to standard of care imaging across multiple centers.

Here, we will determine the final biomarker performance using the dataset collected and reviewed by the core lab. Similar analyses will be run on the VCI biomarker distributions for the Phase 2 subject group as was done in Phase 1. Additionally, subgroup analyses comparing biomarker results across research sites, and age groups, will be conducted to determine if any age or NovaGuide inter-operator variability effects are present in the data (two-way ANOVA with post-hoc comparisons).

Sample size calculation: In Phase 2, we seek to demonstrate stricter confidence bounds on biomarker diagnostic performance in excess of 90% ROC-AUC. Assuming the biomarker is observed to meet that performance threshold, then a sample of approximately 150 LVO subjects in each patient group is required to attain a one-tailed 95% confidence bound on the observed AUC of 3%. That is, the target AUC and sample size would afford 95% confidence that the underlying general population AUC is greater than 87%. Moreover, across five sites, this results in approximately 30 LVO subjects per site, affording sufficient power for detection of moderate potential inter-site effects in the range of Cohen’s $D \geq 0.75$.

Calculate study and site specific stroke workflow times: Stroke workflow parameters and times are well characterized in literature, including “Get with the Guidelines, Stroke” published by the American Heart Association, Inc. and will be utilized as a historical control comparator for data collected in Phase 2. We will use these published stroke guidelines which have mean times for the stroke workflow parameters to show that we are non-inferior to these when using the NovaGuide device. Additionally, the data will be compared to the corresponding randomized group (Cohort C and D)

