11.5 Data Analysis

Evaluation of correlation between diagnostic imaging standard of care and VCI biomarker by an independent core laboratory masked to local radiology determination. Success criteria will include clinical validation of VCI biomarker for LVO detection threshold performance at or exceeding 90% ROC-AUC (targeting SEN & SPE greater than 90%) to standard of care imaging.

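### The Phase 1 sensitivity target has no fixed cut-off and no accompanying specificity value, so it adds nothing to the AUC criterion

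*Combined protocol and SAP*

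**What the plan says.** Section 4.2.1 gives the Phase 1 primary endpoint three components: "Area Under the Curve (AUC), Sensitivity, and Specificity of VCI when compared against standard of care CTA imaging for large vessel occlusion assessment".

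Section 11.1 gives values for two of the three: "Demonstration of VCI diagnostic performance at or exceeding 85% ROC-AUC (targeting SEN greater than 90%) to standard of care imaging". The next paragraph of 11.1, on biomarker analysis, plans to compute "SEN, SPE, and accuracy at various levels of diagnostic threshold, including that corresponding to Youden's maximal J-statistic". It does not say which of those thresholds is used to judge the sensitivity target.

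The specificity targets elsewhere come with a different AUC figure. Section 11.2, for Phase 2, reads "Demonstration of VCI biomarker performance at or exceeding 90% ROC-AUC (targeting SEN & SPE greater than 90%) to standard of care imaging across multiple centers". Section 11.5, repeated in the synopsis, names no phase and sets as its success criterion "LVO detection threshold performance at or exceeding 90% ROC-AUC (targeting SEN & SPE greater than 90%) to standard of care imaging". Both are tied to an AUC of 90%, not to the 85% of Phase 1.

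The Phase 1 sample size in 11.1 rests on AUC alone. About 50 subjects per group are chosen to separate 85% from the 78% attributed to existing scales.

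**The concern.** Sensitivity and specificity move against each other along the ROC curve. A sensitivity target says something about a marker only if the cut-off, or the specificity that goes with it, is fixed beforehand. Section 11.1 fixes neither, so the statement that the target was met would depend on a choice made after the data are seen.

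This matters because section 2 gives Phase 1 the job of establishing baseline performance and defining the context of use for the FDA submission. A Phase 1 report of sensitivity above 90% would read as evidence about the marker, when it could simply reflect a lenient cut-off.

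**Working it through.** **Inputs.** AUC 0.85 and sensitivity 0.90 come from 11.1, as do about 50 subjects per group for precision and 54 per group as the enrolment target. The documents give no distribution for VCI, so the binormal model below is an assumption.

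**The plan's own figure.** Section 11.1 describes a sample of about 50 per group, "which gives a one-tailed 95% confidence bound on the target 85% AUC of less than 7" percent. With the Hanley-McNeil standard error:

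- Q1 = A/(2 − A) = 0.7391 and Q2 = 2A²/(1 + A) = 0.7811, with A² = 0.7225.
- SE = √{[A(1 − A) + 49(Q1 − A²) + 49(Q2 − A²)]/2500} = √{[0.1275 + 49(0.0166) + 49(0.0586)]/2500} = 0.0391.
- 1.645 × 0.0391 = 0.064, so the lower limit is 0.786.

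The figure reproduces, and the limit lies above 0.78. The AUC part of the Phase 1 criterion works as described.

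**Freely chosen cut-off.** Lowering the cut-off raises observed sensitivity until it reaches 100%. Some cut-off therefore gives more than 90% in every data set, whatever the true AUC. For a marker no better than chance, sensitivity of 90% comes with specificity of 10%.

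**Specificity at 90% sensitivity, equal variances.**

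- d = √2 × z(0.85) = 1.414 × 1.036 = 1.466.
- Specificity = Φ(d − z(0.90)) = Φ(1.466 − 1.282) = Φ(0.184) = 57.3%.

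**Unequal variances.** Let s be the ratio of the LVO to the non-LVO standard deviation. The mean difference that gives AUC 0.85 is a = z(0.85)√(1 + s²), and specificity at 90% sensitivity is Φ(a − s·z(0.90)).

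| s | a | a − s·z(0.90) | Specificity |
|---|---|---|---|
| 0.5 | 1.159 | 0.518 | 69.8% |
| 1 | 1.466 | 0.184 | 57.3% |
| 2 | 2.318 | −0.246 | 40.3% |

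**Youden cut-off, equal variances.** Sensitivity = specificity = Φ(d/2) = Φ(0.733) = 76.8%, below the 90% target.

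**Sampling variation.** Both simulations use 54 per group, true AUC 0.85 and the equal-variance model.

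- At the observed Youden cut-off, sensitivity exceeds 90% in at most about 16% of trials. That figure breaks ties toward higher sensitivity; it is lower if ties are broken the other way, or with 50 per group.
- With the cut-off set at the smallest observed sensitivity above 90% (49/54 = 90.7%), observed specificity averages 58%, with 5th and 95th percentiles of 39% and 76%.

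**The case against.** The strongest reply is that 11.1 asks for AUC to be demonstrated and mentions sensitivity only in a parenthesis, as something targeted. The synopsis labels Phase 1 as feasibility, the sample size rests on AUC, and the pivotal claim, with its specificity target, belongs to Phase 2. A lower bar for a feasibility phase is a legitimate choice. This stands, and it limits the point: the target is not a hard pass mark, and the AUC criterion is not undermined.

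It can also be said that sections 11.5 and the synopsis do target specificity. They do, but alongside an AUC of 90%, so they do not complete the 85% statement for Phase 1.

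Three stronger readings are tempting, and the documents do not support them.

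- *The target cannot fail.* This holds only if the cut-off is chosen freely. Section 11.1 does not say that it will be, and at the one cut-off it names the target would usually be missed.
- *Specificity is hidden.* It is part of the primary endpoint, and 11.1 plans to compute it at each threshold. The gap is in the criterion, not in the reporting.
- *Phase 1 could succeed with a marker worse than the clinical scales.* Section 2 reports "SEN and SPE ranging in a recent study from 0.50-0.64 and 0.83-0.92, respectively" for those scales. Setting 57% against 0.83-0.92 mixes operating points, because the scales have sensitivity of only 0.50-0.64. At matched specificity, under the same model, a marker at AUC 0.85 has sensitivity Φ(1.466 − 0.954) = 0.70 at specificity 0.83 and Φ(1.466 − 1.405) = 0.52 at 0.92. Both are at or above the scales' range. Section 2 gives ranges and not pairs, so no exact matched comparison can be made from it.

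**Conclusion.** The concern holds as a defect in how the Phase 1 sensitivity target is specified. As written, the target cannot discriminate between markers, because whether it is met depends on a cut-off the plan leaves open. That cut-off dependence needs no model. The 57% specificity (40-70% across the standard deviation ratios shown) and the 77% Youden sensitivity do rest on the binormal assumption and on a true AUC of exactly 0.85, which is the floor of the criterion; a higher AUC would improve both. The change should be made, but the AUC criterion and its sample size can stand.

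**What to change.** In 11.1, replace the parenthetical sensitivity target with a measure that fixes one axis. Either of these would do:

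- specificity at the cut-off giving 90% sensitivity, with its one-sided 95% lower bound, computed so that it allows for the cut-off being estimated (for example by bootstrap); or
- sensitivity at a specificity stated in advance, with its bound.

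Add that sensitivity at a cut-off picked from the data does not count toward the Phase 1 target. The read-off in the first option follows a rule set beforehand, so it is not such a pick. If a minimum value is wanted, the sponsor should state it before the data are seen. Any comparison with the clinical scales should be made at matched specificity, from paired figures rather than the ranges in section 2.

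The cost is one or two sentences and one extra read-off from an ROC curve already planned, with no new subjects or data. The sensitivity target becomes harder to claim, and at 54 per group the bound will be wide: in the simulation the 5th percentile of observed specificity lies about 19 points below its mean (58 − 39).

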4.4 Study Population Size

Phase 1: Approximately 108 subjects will be randomized to the TCD only group (54 subjects in Cohort A and 54 subjects in Cohort B). An additional 108 subjects will be randomized to the NO TCD group. An interim feasibility and safety assessment will be completed after Phase 1.

Phase 2: Approximately 312 subjects presenting with stroke like symptoms for which diagnostic imaging has been ordered will be enrolled (156 in Cohort A and 156 in Cohort B). Primary and secondary endpoints will be calculated after completion of Phase 2.

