4.16.2 Lucid M1 System Scanning Technique (Traditional TCD)

If traditional TCD is conducted using the Lucid M1 System alone, measurements will be collected in the MCA at multiple depths ranges between 45 to 65 mm. The MCA scans will be collected from the trans-temporal window by positioning the probe superior to the zygomatic arch. Once cerebral blood flow velocity (CBFV) of the target vessel is found, the TCD operator will hold this position to record 30 seconds of data.

Cohort A TCD will be subjects identified per CTA findings in the Emergency Room (ER), Stroke Care Unit or Imaging Unit as having a large vessel occlusion. A single TCD scan will be collected by a designated TCD operator using the NovaGuide System or the Lucid M1 System alone (manual TCD). The TCD scan will be collected following CTA within a three (3) hour window and prior to standard of care stroke treatment (e.g., mechanical thrombectomy). Note, tPA can be administered prior to TCD measurements. Study measurements will not delay nor interfere with the patients' standard of care treatment. No follow-up scans will be collected.

Cohort B TCD will be subjects identified per CTA findings in the Emergency Room (ER), Stroke Care Unit or Imaging Unit as having a non-large vessel occlusion. A single TCD scan will be collected by a designated TCD operator using the NovaGuide Robotic System or the Lucid M1 System alone (manual TCD). These scans will be collected within a 24-hour period after enrolment and no follow-up scans will be collected.

Cohort C NO TCD will be subjects identified per CTA findings in the Emergency Room (ER), Stroke Care Unit or Imaging Unit as having a large vessel occlusion. No TCD scans will be conducted and subjects followed through to discharge.

Cohort D NO TCD will be subjects identified per CTA findings in the Emergency Room (ER), Stroke Care Unit or Imaging Unit as having a non-large vessel occlusion. No TCD scans will be conducted and subjects followed through to discharge.

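### Raw accuracy in a sample fixed at about 50% LVO is just (SEN+SPE)/2: it does not estimate accuracy among patients suspected of LVO, and for some operating points it ranks VCI and the clinical scales differently

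*Combined protocol and SAP*

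**What the plan says.** Section 11.1 computes ROC-AUC for VCI "for comparison to standard of care imaging (CTA) and prehospital/neurological clinical scales", and the same sentence continues "along with SEN, SPE, and accuracy at various levels of diagnostic threshold", one of the thresholds being Youden's. Section 11.2 says "Similar analyses will be run on the VCI biomarker distributions for the Phase 2 subject group as was done in Phase 1". Comparison with clinical scales is a secondary endpoint in both phases (sections 4.2.1 and 4.2.2), but no metric is named there.

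The case mix is set by design. Section 4.4 gives the Phase 1 TCD group as "54 subjects in Cohort A and 54 subjects in Cohort B" and Phase 2 as "156 in Cohort A and 156 in Cohort B". LVO status is known before entry: "Cohort A TCD will be subjects identified per CTA findings" (section 4.16.2; the criteria in 4.6.1 and 4.6.2 agree).

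Section 2 presents VCI as a prehospital aid to triage and transfer when LVO is suspected. It describes the existing scales as having "SEN and SPE ranging in a recent study from 0.50-0.64 and 0.83-0.92, respectively". Nowhere do the documents state the share of LVO in that setting, re-weight accuracy to it, or plan PPV or NPV.

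**The concern.** Sensitivity and specificity are each calculated within one disease group, so the ratio of the two groups does not enter them. Accuracy pools the groups and depends directly on that ratio. Here the ratio is an enrolment quota and says nothing about how common LVO is among the patients in whom the test would be used.

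The two kinds of test also differ in profile. VCI is aimed at high sensitivity: the Phase 1 target in section 11.1 is SEN above 90%, with no SPE target. The scales in section 2 have low sensitivity and high specificity. Giving sensitivity half the weight therefore moves a VCI-versus-scale comparison toward VCI relative to any setting with less than half LVO. A reported accuracy lead could then be partly a product of the quota. Section 2 already faults the scales for low accuracy, so such a figure would readily be read as a comparative claim.

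**Working it through.** **Plan's own figures.** The documents state no accuracy value, so there is none to reproduce. The AUC precision statements beside it do reproduce with the Hanley–McNeil standard error, SE² = [A(1−A) + (n−1)(Q1−A²) + (n−1)(Q2−A²)]/n², where Q1 = A/(2−A) and Q2 = 2A²/(1+A). For A = 0.85 and n = 50 per group, 1.645 × SE = 6.4 points (section 11.1 says under 7). For A = 0.90 and n = 150, it is 3.04 points (section 11.2 says 3). Nothing below alters these.

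**Step 1: the identity.** Accuracy(p) = p×SEN + (1−p)×SPE, with p the LVO share.
- At 54/(54+54) or 156/(156+156), p = 0.5 and accuracy = (SEN+SPE)/2.
- With J = SEN+SPE−1 this is (J+1)/2, so at Youden's threshold it adds nothing to J.
- If one Phase 1 cohort stops at 49 (90% of 54 is 48.6), p is 47.6% or 52.4%. The largest shift among the operating points tried is 0.0243 × (0.92 − 0.50) = 0.010, so the identity holds to about 1 point.

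**Step 2: an illustrative pair.** The VCI point 90/80 is assumed. The scale point 64/92 joins the upper ends of the two ranges in section 2; that pairing is also assumed. The prevalence range of 5–40% is assumed.

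| LVO share | VCI 90/80 | Scale 64/92 |
|---|---|---|
| 50% | 85.0% | 78.0% |
| 40% | 84.0% | 80.8% |
| 30% | 83.0% | 83.6% |
| 20% | 82.0% | 86.4% |
| 10% | 81.0% | 89.2% |
| 5% | 80.5% | 90.6% |

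Break-even: 0.80 + 0.10p = 0.92 − 0.28p, so p = 0.12/0.38 = 31.6%.

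**Step 3: VCI at the Phase 1 target.** Assume an equal-variance binormal ROC. AUC 0.85 gives d = √2 × z(0.85) = 1.466, and at SEN 0.90 SPE = Φ(1.466 − 1.282) = 0.573.

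| LVO share | VCI 90/57.3 | Scale 50/92 | Scale 64/83 | Scale 64/92 |
|---|---|---|---|---|
| 50% | 73.7% | 71.0% | 73.5% | 78.0% |
| 20% | 63.8% | 83.6% | 79.2% | 86.4% |
| 10% | 60.6% | 87.8% | 81.1% | 89.2% |

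With crossover = ΔSPE/(ΔSPE + ΔSEN), VCI falls behind the 50/92 scale below 46.4% LVO and behind the 64/83 scale below 49.7%. Its leads over them at 50% are small (2.7 and 0.2 points). The 64/92 scale leads VCI already at 50%, so there is no reversal against it.

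**Step 4: VCI at the Phase 2 target.** With SEN = SPE = 0.90:
- against 50/92, crossover = 0.02/(0.02+0.40) = 4.8%;
- against 64/92, crossover = 0.02/(0.02+0.26) = 7.1%;
- against a scale with SPE 0.83, VCI is better on both measures and no crossover exists.

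**The case against.** The strongest reply is that accuracy decides nothing in this plan. The endpoints and success criteria are AUC, SEN and SPE, and the superiority argument in section 11.1 is made on AUC (85% against 78%). Grammatically, the comparison with scales attaches to ROC-AUC, with accuracy listed beside it. That section 11.2 repeats the accuracy figure is a reading of its reference to similar analyses. SEN and SPE are reported at the same thresholds, so a careful reader can re-weight. All of this stands and limits the point to reporting and interpretation.

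Two stronger readings are tempting, and the documents do not support them.

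- A reader might infer that the 1:1 sample favours VCI whatever its true performance. Step 3 contradicts this: a 64/92 scale beats VCI at 90/57.3 even at 50% LVO. The reversal in Step 2 also depends on an assumed VCI point. Under the binormal model, 90/80 implies AUC of about 0.93, above both AUC targets, yet it misses the Phase 2 SPE target.
- A reader might infer that the 50% ranking is the wrong one for triage. That treats accuracy at triage prevalence as the truth, which costs a missed LVO and a false alarm equally. At 10% LVO, calling everyone negative scores 90%, above the 89.2% of the 64/92 scale. If a miss counts (1−p)/p times a false alarm, the 50:50 ranking is the correct one. The plan states no such weighting, so neither ranking can be called right from the documents.

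What the reply does not remove is that a planned figure takes its value from the quota and is neither labelled as balanced accuracy nor tied to a prevalence. The plan also does not say whether the scales are scored in the same subjects (the schedule in section 4.15 lists only the NIHSS) or taken from literature. In the latter case, VCI accuracy at 50% LVO could be set beside accuracy from another case mix.

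**Conclusion.** The concern holds in a limited form. Raw accuracy as planned equals (SEN+SPE)/2, within about 1 point under the allowed enrolment shortfall, and does not estimate accuracy among patients suspected of LVO. Below 50% LVO it leans toward the more sensitive test relative to that setting. Whether this changes a ranking depends on the operating points: it can do so at moderate prevalence in the illustrative pair and against some scales at the Phase 1 target, but hardly at all if Phase 2 meets both of its 90% targets.

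The sizes rest on an assumed prevalence range, assumed pairings of the scale figures and, in Step 3, the binormal model. The identity needs none of these. No success criterion or sample size changes. The correction is worth making because the figure is planned, sits beside a listed secondary comparison, and would be read in a programme aimed at regulatory submission.

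**What to change.** In section 11.1, and explicitly in 11.2, replace raw accuracy with three quantities calculated from SEN and SPE over a stated range of LVO prevalence p, for VCI and the scales alike:
- accuracy = p×SEN + (1−p)×SPE;
- PPV = p×SEN/[p×SEN + (1−p)(1−SPE)];
- NPV = (1−p)×SPE/[(1−p)×SPE + p(1−SEN)].

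If the 50% figure is kept, label it balanced accuracy, (SEN+SPE)/2, and compare tests on SEN and SPE. State whether the scale values come from the same subjects or from literature.

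Add two cautions. First, SPE is estimated in a Cohort B that excludes haemorrhage and occlusions of other large arteries, such as the basilar and vertebral (section 4.6.2), so the re-weighted figures apply to that case mix and not to all suspected stroke. Second, the Screening/Enrollment log (section 4.7) can supply a prevalence value only if it records LVO status for everyone pre-screened, which the protocol does not say.

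The cost is SAP wording and a short calculation, with no new data unless the log is to supply prevalence and lacks LVO status. The downside is that the reported accuracy may be less favourable and will depend on a stated prevalence range.
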